Molecular Subtyping of Extensive Stage Small Cell Lung
Cancer and Relevant Clinical Significance
(The MOSAIC study)

2022.3.29

Version 1.0

Objective:

- (1) Validating the predictive value of transcriptome-based molecular subtyping of extensive stage small cell lung cancer(SCLC) for the efficacy of PD-1/PD-L1 inhibitor in the first line setting.
- (2) Exploring the differences of immune microenvironment between different SCLC subtypes to reveal the mechanisms of immunotherapy resistance of SCLC

Protocol:**1.1 Design**

This study is a retrospective observational study without intervention in clinical treatment. In prior study, the transcriptomic data was used to classify SCLC into four subtypes, which might have different sensitivity to immunotherapy. Therefore, molecular subtyping could be used as an important biomarker for predicting efficacy of immunotherapy, which need further validation. This study will explore the predictive value of different subtypes of SCLC for immunotherapy and mechanisms of immunotherapy resistance of SCLC. Extensive stage SCLC patients receiving first-line standard treatment will be enrolled in this study. Baseline tumor tissue samples and peripheral blood samples will collected for transcriptome and immunohistochemistry analysis etc. Based on these results, patient will be classified into four subtypes and efficacy and safety of treatment will be recorded. We will compare the efficacy between different subtypes of SCLC and analyze whether molecular typing could predict the efficacy of immunotherapy; Compare the differences in immune microenvironment of different subtypes of SCLC to reveal the mechanism of immunotherapy resistance. The treatment regimen involved in this study follows guidelines for the first-line treatment of extensive stage SCLC: cisplatin+etoposide or carboplatin+etoposide with or without approved PD-(L)1 inhibitor for SCLC. Treatment options are determined by the patient's supervising physician.

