1.4 Sample Size

Chemotherapy: 80-100 cases.

Immunotherapy+chemotherapy: 80-100 cases.

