1.5 Statistics

All measurements will be expressed as mean \pm standard deviation. COX regression analysis was used to examine the correlation between immune indicators and efficacy, and one-way ANOVA will be used to analyze the correlation between the variables and the efficacy of immunotherapy or adverse effects. The number of different cell types will be compared between patient subgroups using the Wilcoxon rank-sum and Jonckheere-Terpstra tests. Differences between the two groups will be analyzed using a two-sided t-test. Categorical variables and continuous variables will be calculated according to frequency counts and median values respectively. The statistical analysis software is GraphPad Prism and SPSS 19.0. $P < 0.05$ will be considered statistically different.

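### Objective 2 reads a resistance mechanism from a between-subtype comparison, and the outcome analyses in 1.5 cannot tell immunotherapy resistance from prognosis

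*Combined protocol and SAP*

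**What the plan says.** The inference is stated twice. Objective (2) reads "Exploring the differences of immune microenvironment between different SCLC subtypes to reveal the mechanisms of immunotherapy resistance of SCLC", and section 1.1 repeats it: "Compare the differences in immune microenvironment of different subtypes of SCLC to reveal the mechanism of immunotherapy resistance". Section 1.5 gives the test for cell counts: "The number of different cell types will be compared between patient subgroups using the Wilcoxon rank-sum and Jonckheere-Terpstra tests". The subgroups are not defined there.

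Section 1.5 also has two analyses that involve outcome. One is "COX regression analysis was used to examine the correlation between immune indicators and efficacy"; the other is "one-way ANOVA will be used to analyze the correlation between the variables and the efficacy of immunotherapy or adverse effects". Neither refers to Objective 2, and neither states a comparison between regimens.

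A comparator group is available. Section 1.4 lists "Chemotherapy: 80-100 cases" and the same number on immunotherapy plus chemotherapy. PFS is the primary endpoint (1.3). The treating physician chooses the regimen (1.1).

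**The concern.** Resistance to immunotherapy is a statement about how a feature changes the benefit of a treatment. The comparison meant to reveal it takes only baseline subtype and baseline immune measurements. Subtypes are defined from the tumour transcriptome, so their immune features may well differ whether or not those features affect PD-(L)1 benefit.

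Adding the Cox and ANOVA lines helps only in part. They can screen out a feature unrelated to outcome. They cannot screen out a feature that predicts shorter PFS on any regimen. At stake is the conclusion of a stated objective: a subtype marker or a general prognostic factor could be published as a mechanism of immunotherapy resistance. The primary endpoint and patient safety are not affected.

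**Working it through.** **Inputs from the documents.** 80-100 patients per group, so 80 + 80 = 160 to 100 + 100 = 200 in all (1.4); four subtypes, shares not given (1.1); PFS (1.3); a 0.05 threshold (1.5). The plan states no power, effect size, event count or error rate, so there is no figure of its own to reproduce.

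**Step 1: what each planned analysis uses.**

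| Analysis | Immune feature | Outcome | Contrast with chemotherapy |
|---|---|---|---|
| Subtype comparison (Objective 2, 1.1) | yes | no | no |
| Wilcoxon and Jonckheere-Terpstra (1.5) | yes | none named | none stated |
| Cox (1.5) | yes | yes | none stated |
| One-way ANOVA (1.5) | 'variables', undefined | yes, on immunotherapy | none stated |

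**Step 2: what has to be estimated.** Let x be the feature in SD units and T = 1 for immunotherapy plus chemotherapy. Write

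log h(t) = log h0(t) + b1·x + b2·T + b3·x·T.

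The feature's log hazard ratio is b1 on chemotherapy and b1 + b3 on immunotherapy plus chemotherapy. Modification of PD-(L)1 benefit is b3. The subtype comparison estimates none of these. A Cox model within the immunotherapy group tests b1 + b3, and a pooled main effect tests a mixture of b1 and b1 + b3. Both are non-zero when b3 = 0 and b1 is not.

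**Step 3: simulation.** Two simulations were run, with 600 and 1,000 studies per setting. Assumptions not in the documents: half the patients on each regimen with no confounding; one subtype shifted by a given number of SDs; subtype shares equal or unequal (40/25/20/15%; the second simulation also used 50/20/15/15% for the rank tests); exponential PFS with median 5.5 or 5 months on chemotherapy; treatment hazard ratio 0.75; uniform censoring over 6-30 or 6-40 months. Kruskal-Wallis stands in for the planned rank tests.

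*Prognostic-only feature* (hazard ratio 0.75 per SD in both groups, b3 = 0), proportion significant at 0.05:

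| Test | First simulation | Second simulation |
|---|---|---|
| Cox, immunotherapy group alone | 60-74% | 63-72% |
| Cox, pooled | 89-96% | 92-96% |
| Feature-by-treatment interaction | 3-7% | 5-6% |

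In the second simulation, requiring both a subtype difference (0.8 SD shift) and a Cox association in the immunotherapy group still flags this feature in 60-72% of studies.

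*Feature with no bearing on outcome*, flagged by the subtype comparison alone:

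| Shift in one subtype | Flagged |
|---|---|
| 0 | 3-6% |
| 0.3 SD (second simulation only) | 15-28% |
| 0.5 SD | 38-72% |
| 0.8 SD | 80-99% |
| 1.0 SD | 96-100% |

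For the 0.8 SD shift, also requiring a Cox association in the immunotherapy group lowers this to about 5%.

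Counting any pairwise difference over 5 features and 6 subtype pairs (5 × 6 = 30 tests) gives 64-69% even with no shift. That is multiplicity, so it is not used as evidence here.

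**Step 4: hand check.** For a standardised feature and D events, SE(b1) ≈ 1/√D, and with events split equally SE(b3) ≈ √(4/D). D is taken from one simulated study per setting.

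- Pooled main effect, D = 144 (160 patients): |ln 0.75| × √144 = 0.288 × 12 = 3.45; power = Φ(3.45 − 1.96) = 93%, against 92% simulated.
- Interaction hazard ratio 0.7, D = 139 (160 patients): 0.357/√(4/139) = 0.357/0.170 = 2.10; power = Φ(0.14) = 56%, against 55%.
- The same at 200 patients, D = 175: 0.357/0.151 = 2.36; power = Φ(0.40) = 66%, against 64%.
- Interaction hazard ratio 0.6, D = 135 and 171: 0.511/0.172 = 2.97 and 0.511/0.153 = 3.34; power 84% and 92%, against 81% and 91%.

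**The case against.** The strongest reply is that the sentence in 1.1 is a chain. Its first half compares efficacy between subtypes and asks whether subtype predicts immunotherapy benefit; the second half then looks at how the microenvironments differ. On that reading, outcome and treatment enter through the subtype. This is a fair reading, but Objective 2 is not made conditional on that result. Even if one subtype benefits less, every feature that differs in that subtype lines up with resistance, and the comparison cannot say which one matters.

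Other points stand and limit the concern:

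- A reader might infer that immune features are never related to outcome. The documents do not support that, because the Cox and ANOVA lines do so, and the ANOVA line names immunotherapy. What is missing is the link to Objective 2 and the contrast with chemotherapy.
- A reader might infer that the plan will usually name a false mechanism. That depends on effect sizes, subtype shares and feature counts that the documents do not give. At 0.3 SD a single irrelevant feature is flagged in only 15-28% of studies. No rule in the plan says that a significant subtype difference is a mechanism.
- A reader might infer that the chemotherapy patients are left out of the immune analyses. The Cox line is restricted to neither group; the plan is silent.
- Objective 2 is worded as exploratory. That softens it, but 'reveal' still promises more than the comparison can deliver.
- The simulated 3-7% for the interaction assumes no confounding. With physician-chosen treatment it may not carry over without adjustment.

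**Conclusion.** The concern holds as a gap between the stated conclusion and the planned analyses. The subtype comparison cannot by itself support a mechanism claim, and joining it to the Cox or ANOVA line does not close the gap, because no contrast between regimens is stated. For a prognostic-only feature, mislabelling would be the more likely outcome: a significant main effect in about 60-74% of studies within the immunotherapy group and 89-96% pooled. These sizes rest on the assumed hazard ratio of 0.75 per SD, the assumed PFS and censoring, and 160-200 patients. The ANOVA line was not simulated; it fails for the same structural reason. The argument in Step 2 needs none of these assumptions. The change is worth making because it affects a stated objective and uses data already planned.

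**What to change.** In 1.5, for the immune features examined under Objective 2, fit a Cox model for PFS in all patients with feature, treatment and feature-by-treatment interaction. Adjust for recorded baseline prognostic factors such as ECOG score and age, because treatment is physician-chosen. Report the interaction estimate with its 95% CI and the feature's hazard ratio in each treatment group, with a false-discovery-rate adjustment across features. Label a feature with similar hazard ratios in both groups as prognostic. Treat the results as hypothesis-generating, not as a strict significance gate.

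In Objective (2) and 1.1, call between-subtype differences descriptive, and replace the promise to reveal the mechanism with the aim of identifying candidate markers of resistance. If the interaction model is not adopted, the minimum change is to state that Objective 2 is descriptive and hypothesis-generating.

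The cost is wording in three places and one model per feature, with no new data. The downside is power: about 55-64% for an interaction hazard ratio of 0.7 per SD and 81-91% for 0.6, before any multiplicity adjustment. Some real modifiers will be missed and the claim will be more modest.

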1.2 Patients**Inclusion Criteria:**

- 1) Male or female, aged 18 to 100 years
- 2) Patients with untreated advanced small cell lung cancer clearly diagnosed by histopathology
- 3) Be able to provide tumor biopsy tissue sample for molecular analysis
- 4) ECOG score: 0 ~2;
- 5) Expected survival of more than 3 months.
- 6) Has at least 1 measurable or evaluable tumor lesion with a longest diameter ≥ 10 mm at baseline (in case of lymph nodes, a shortest diameter ≥ 15 mm is required) according to RECIST v1.1
- 7) Received first-line chemotherapy or chemotherapy + PD-(L)1 inhibitor and be able to provide complete treatment information and efficacy evaluation results.
- 8) Voluntary signed informed consent and expected good compliance.

Exclusion Criteria:

- 1) Patient unable to tolerate chemotherapy.
- 2) Patients unable to provide tumor tissue samples for testing
- 3) Patients with other malignant tumors or a history of other malignant tumors
- 4) Patients have any other reason to be unfit to participate in this study.

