1.3 Endpoint and follow up

Primary endpoint: Progression-free survival

Secondary endpoint: Overall survival; Objective response rate; molecular subtyping and tumor microenvironment biomarkers.

Follow-up plan:

- 1) Patients will be reviewed every 2 cycles during treatment to assess effectiveness and record vital signs and test results.
- 2) Patients will be reviewed periodically every 3 months after completion of treatment until disease progression.
- 3) After disease progression, patients will continue to be followed up every 3 months to record post treatment until die or lost follow-up.

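### Treatment is the physician's choice and section 1.5 names no baseline adjustment, so within-subtype treatment effects, and under certain conditions the treatment-by-subtype contrast, are open to confounding by indication

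*Combined protocol and SAP*

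**What the plan says.** Section 1.1 describes a retrospective, non-interventional study. The regimen is "cisplatin+etoposide or carboplatin+etoposide with or without approved PD-(L)1 inhibitor for SCLC", and "Treatment options are determined by the patient's supervising physician". Objective (1) is "Validating the predictive value of transcriptome-based molecular subtyping" for first-line PD-1/PD-L1 inhibitor efficacy, and section 1.1 adds that the study will "analyze whether molecular typing could predict the efficacy of immunotherapy". Section 1.4 sets a chemotherapy cohort of 80-100 and a second cohort: "Immunotherapy+chemotherapy: 80-100 cases". Section 1.3 gives "Primary endpoint: Progression-free survival".

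Eligibility in section 1.2 is wide on age ("Male or female, aged 18 to 100 years") and admits ECOG 0, 1 and 2. It narrows prognosis in two ways: a life expectancy above 3 months is required, and patients who cannot tolerate chemotherapy are excluded.

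Section 1.5 lists a Cox regression tied to immune indicators, one-way ANOVA, Wilcoxon rank-sum and Jonckheere-Terpstra tests, and a two-sided t-test between two groups that it does not define. It also plans counts and medians as descriptive summaries. It does not rule out covariates in the Cox model, but it names none. No section mentions stratification, matching, weighting or a sensitivity analysis for confounding.

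**The concern.** A subtype is predictive for the PD-(L)1 inhibitor only if the drug's effect differs between subtypes. That is why the chemotherapy cohort matters: the question is how the treatment HR changes from one subtype to another.

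If prognosis influenced the physician's choice, each within-subtype treatment HR mixes prognosis with drug effect. Whether this carries through to the contrast between subtypes depends on how the selection is distributed. It can create an apparent subtype difference or hide a real one. The listed analyses contain no step that would correct it. If covariates are chosen only after the data are seen, the choice is itself open to question.

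Two limits apply. An overall drug effect is not a stated objective and is not at issue here. Comparing subtypes inside one treatment cohort is not exposed in the same way, because treatment is then constant.

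**Working it through.** The plan gives no derived figure to reproduce: section 1.4 states cohort sizes without power, effect size or event count. The size below is an illustration.

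**Inputs from the documents:** 80-100 per cohort (1.4), four subtypes (1.1), ECOG 0-2 (1.2), PFS as endpoint (1.3).

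**Assumed inputs:** 90 per cohort, equal subtypes, exponential PFS with median 5.5 months, uniform 6-30 month censoring (about 87% events), and ECOG 2 as the only factor with a true prognostic effect.

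**1. Closed form for one omitted binary factor.** With prognostic HR *g* and prevalences p_IO (PD-(L)1 cohort) and p_C (chemotherapy cohort), a true treatment HR of 1 appears as [p_IO(g−1)+1] / [p_C(g−1)+1].
- Moderate (10% vs 30%, g = 1.5): 1.05/1.15 = 0.91.
- Strong (10% vs 40%, g = 2): 1.10/1.40 = 0.79.

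The contrast between two subtypes is the ratio of their factors, so equal factors cancel. Simulated values lie somewhat nearer 1 because high-risk patients leave the risk set early.

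**2. Simulation, 4,000 datasets per scenario.** The unadjusted Cox model has 7 terms: treatment, 3 subtype, 3 interaction. The adjusted model adds age, sex, ECOG 1 and ECOG 2, making 11. The ratio is one subtype against the mean of the other three. Prevalences are chemotherapy vs PD-(L)1. Monte Carlo error is about 0.4 points at 6% and 0.7 at 27%.

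| ECOG 2 prevalence, HR | Ratio, unadjusted → adjusted | Rejection, unadjusted → adjusted |
|---|---|---|
| None: 25% v 25%, HR 2 | 1.005 → 1.005 | 5.5% → 6.0% |
| Every subtype 30% v 10%, HR 1.5 | 0.996 → 0.998 | 5.9% → 6.4% |
| Every subtype 40% v 10%, HR 2 | 1.003 → 1.002 | 5.2% → 5.2% |
| One subtype 30% v 10%, HR 1.5 (moderate) | 0.928 → 1.005 | 6.0% → 6.2% |
| One subtype 40% v 10%, HR 2 (strong) | 0.834 → 1.005 | 8.4% → 6.0% |
| True ratio 0.60, no imbalance | 0.606 → 0.583 | 25.0% → 27.8% |
| True ratio 0.60, one subtype 10% v 30%, HR 1.5 | 0.637 → 0.578 | 21.6% → 28.8% |
| True ratio 0.60, one subtype 10% v 40%, HR 2 | 0.740 → 0.586 | 12.7% → 27.5% |

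The within-subtype HR in the affected subtype (true value 1) goes from 0.929 to 1.007 on adjustment in the moderate case and from 0.830 to 1.001 in the strong case. With equal strong selection in every subtype it is still 0.83 unadjusted and 0.99 adjusted, although the interaction ratio is clean.

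**3. Bias against precision.** Moderate: 0.075/0.374 = 0.20 of a standard error. Strong: 0.182/0.371 = 0.49. With *e* events per cell, the contrast's SE is √(2/e + 2/(3e)). At an assumed 85% event rate:
- 20 patients per cell: e = 17, SE 0.396, CI factor exp(1.96 × 0.396) = 2.17.
- 25 patients per cell: e = 21.25, SE 0.354, CI factor 2.00.

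**4. Equal selection, unequal prognostic effect.** With 15% vs 35% in every subtype and g = 2.5 in one subtype and 1.5 in another, the closed form gives 0.803/0.915 = 0.88. A large-sample simulation (40% vs 10% in every subtype, g = 2.5 in one and 1.5 elsewhere) gives about 0.89-0.90 unadjusted and 0.86 with a common ECOG term. It returns to 1.00 only with an ECOG-by-subtype term.

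**5. If physicians did not know the subtype.** Suppose choice depends on ECOG alone: 20% of ECOG 2 patients and 60% of others receive the inhibitor, with g = 2. A spurious ratio then arises only because ECOG 2 prevalence differs between subtypes. It is 0.95 for prevalences of 20% vs 30%, 0.91 for 15% vs 35%, and 0.86 only at 10% vs 40%.

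**The case against.** Several counter-arguments have force.

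- **No mechanism is documented.** Subtype comes from study assays in a retrospective design, and nothing says physicians knew it. A reader might infer that treatment was chosen by subtype, or that the results are confounded; the documents support neither. This makes the strong case look near an extreme. It does not protect the within-subtype HRs.
- **Equal selection cancels.** It does in the contrast, provided the confounder's effect is the same in every subtype. A reader might take that as a general reassurance; step 4 shows that it is not.
- **Imbalance would be visible.** The descriptive summaries in 1.5 might show imbalance by treatment, so it would be wrong to say that nothing in the plan could reveal it. They are not specified by treatment within subtype, and they correct nothing.
- **Imprecision dominates.** This stands. In the moderate case false positives are 6.0% unadjusted and 6.2% adjusted, and part of the power gain in the masking rows appears without any imbalance (25.0% to 27.8%). The 3-df joint test hardly changes: 6.2% to 6.3% (moderate), 7.8% to 6.9% (strong).
- **The adjusted 1.00 is built in.** ECOG is the only true factor and the model contains it. The simulation shows what a correct model does, not that age, sex and ECOG would remove all confounding here.
- **No interaction model is written.** That is a separate gap. This point concerns the baseline terms that any such model needs.

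**Conclusion.** The point holds in a limited form. Treatment is physician-chosen and section 1.5 names no baseline factor, so within-subtype PD-(L)1 effects are open to confounding by indication. The treatment-by-subtype contrast is open to it under either of two conditions: the prognostic mix by treatment differs across subtypes, or a confounder's effect does. Otherwise the bias largely cancels.

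On assumed inputs the spurious ratio is about 0.93 to 0.83, the latter near an extreme. The main consequence is a shifted estimate rather than many extra false positives. In the strong masking case, power falls to 12.7%, against 27.5% with adjustment. The direction and size of any real selection cannot be derived from the documents. The change is worth making because it bears on the study's first objective and costs little, not because bias has been demonstrated.

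**What to change.** In section 1.5, analyse PFS (and OS) in a Cox model with treatment, four-level subtype and their interaction, adjusted for prespecified baseline age, sex and ECOG (0, 1, 2). Report the interaction HR ratios and the adjusted within-subtype HRs with 95% CIs, and the 3-df joint test. Tabulate age, sex and ECOG by treatment within each subtype. Add a sensitivity model with an ECOG-by-subtype term. Describe the result as an adjusted observational association with residual confounding possible.

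Optional further sensitivity analyses:
- baseline lesion size, which may be missing for some patients because criterion 6 reads "Has at least 1 measurable or evaluable tumor lesion";
- calendar year, over years when both treatments were in use;
- platinum agent, as a proxy only, since it is part of the chosen regimen;
- propensity weighting, with a check for extreme weights.

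**Cost.** Age, sex and ECOG all appear in the inclusion criteria, so no new data should be needed. In the illustration the interaction SE widens by about 2-4% (0.371 to 0.379 with no imbalance, 0.382 to 0.397 at most), and the 3-df test's error rate with no imbalance is 6.8% adjusted against 5.9% unadjusted. At an assumed 85% event rate, 11 parameters leave 136/11 = 12.4 events each at N = 160 and 170/11 = 15.5 at N = 200. At 70% events and N = 160 the figure is 112/11 = 10.2. A full ECOG-by-subtype term adds 2 × 3 = 6 parameters, giving 136/17 = 8.0 to 170/17 = 10.0, which is why it belongs in a sensitivity model. The remaining cost is the added wording and tables.

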1.2 Patients**Inclusion Criteria:**

- 1) Male or female, aged 18 to 100 years
- 2) Patients with untreated advanced small cell lung cancer clearly diagnosed by histopathology
- 3) Be able to provide tumor biopsy tissue sample for molecular analysis
- 4) ECOG score: 0 ~2;
- 5) Expected survival of more than 3 months.
- 6) Has at least 1 measurable or evaluable tumor lesion with a longest diameter ≥ 10 mm at baseline (in case of lymph nodes, a shortest diameter ≥ 15 mm is required) according to RECIST v1.1
- 7) Received first-line chemotherapy or chemotherapy + PD-(L)1 inhibitor and be able to provide complete treatment information and efficacy evaluation results.
- 8) Voluntary signed informed consent and expected good compliance.

Exclusion Criteria:

- 1) Patient unable to tolerate chemotherapy.
- 2) Patients unable to provide tumor tissue samples for testing
- 3) Patients with other malignant tumors or a history of other malignant tumors
- 4) Patients have any other reason to be unfit to participate in this study.

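### Three undated judgement criteria in a study labelled retrospective would let early deaths be excluded in hindsight if eligibility is settled after outcomes are known

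*Combined protocol and SAP*

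**What the plan says.** Section 1.1 states the design: "This study is a retrospective observational study without intervention in clinical treatment". Inclusion 7 in Section 1.2 fits that label. It asks that first-line treatment has been received and that the patient "be able to provide complete treatment information and efficacy evaluation results".

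The same section contains three items that rest on someone's opinion:

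- Inclusion 5: "Expected survival of more than 3 months".
- Inclusion 8, second half: "expected good compliance".
- Exclusion 4: "Patients have any other reason to be unfit to participate in this study".

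None of the three has a time at which it is judged, a named assessor, a prognostic tool or a documentation rule. The plan has no consecutive-case rule and no exclusion log. The independent auditors in Section 1.6 cover efficacy evaluation; eligibility is not mentioned.

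Other wording reads as prospective. Inclusion 2 is "Patients with untreated advanced small cell lung cancer clearly diagnosed by histopathology". Section 1.1 adds "Extensive stage SCLC patients receiving first-line standard treatment will be enrolled in this study". Inclusion 8 requires signed consent, and Section 1.3 sets reviews every 2 cycles and follow-up until death or loss.

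**The concern.** These are the usual entry criteria of a prospective trial, where the investigator judges prognosis without knowing what will happen. If eligibility is settled from the chart after treatment, the same words work differently. A patient who died at six weeks is easily judged not to have had three months' expected survival, or to have been unfit. Selection then depends on the outcome.

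PFS is the primary endpoint and OS is secondary (Section 1.3), and early deaths count in both. Regimen is chosen by the physician (Section 1.1), so nothing makes such exclusions equal across the chemotherapy and chemo-immunotherapy cohorts. Exclusions that are never logged cannot be repaired in the analysis.

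**Working it through.** **1. Can outcome be known when eligibility is judged?** The retrospective label and Inclusion 7 say yes: a patient qualifies only once treatment has been given and efficacy results exist. The untreated-at-entry wording, the future-tense enrolment and follow-up until death say no. The plan does not settle which reading applies, so hindsight is possible but not stated.

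**2. Do other rules already remove these patients?** Partly. Under Inclusion 7, a patient who dies before any response assessment may fail for lack of results. Under Inclusion 8, a patient who dies before consent is sought cannot sign, and no waiver or proxy is mentioned. What remains is a patient who consented, had an assessment after two cycles and then died before month 3. That patient passes Inclusion 7 and consent, and could still be removed under Inclusion 5 or Exclusion 4.

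**3. How large could the effect be?** The plan gives no median, effect size, power or event count, so it has no figure of its own to reproduce. Assumptions: exponential OS with median m of 8 to 14 months; PFS as the earlier of progression and death, with an assumed median of 5 months; no true difference between groups.

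The share dying before 3 months is 1 − s, where s = 0.5^(3/m). At m = 12, s = 0.5^0.25 = 0.841, so 15.9% die. By memorylessness, removing all of them everywhere moves the median OS to m + 3.

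If all are removed from one group only, that group has no events before month 3, and the two groups have equal numbers at risk afterwards. With full follow-up, the large-sample Cox hazard ratio θ then solves

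θ·ln[(1 + θs) / (s(1 + θ))] + 2θ/(1 + θ) = 1.

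At m = 12 with θ = 0.847, the terms are 0.083 + 0.917 = 1.00. Half removal was solved numerically from the matching score equation. The PFS values come from simulating 2,000,000 patients per scenario without censoring.

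| Median OS (months) | Deaths before 3 months | Of 80 / of 100 | Median OS if all removed everywhere | OS HR, all removed from one group | OS HR, half removed from one group | PFS HR, all / half |
|---|---|---|---|---|---|---|
| 8 | 22.9% | 18.3 / 22.9 | 11 | 0.785 | 0.896 | 0.798 / 0.905 |
| 10 | 18.8% | 15.0 / 18.8 | 13 | 0.821 | 0.913 | 0.837 / 0.921 |
| 12 | 15.9% | 12.7 / 15.9 | 15 | 0.847 | 0.925 | 0.863 / 0.932 |
| 14 | 13.8% | 11.0 / 13.8 | 17 | 0.867 | 0.935 | 0.884 / 0.943 |

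The columns of 80 and 100 use the cohort sizes in Section 1.4. Cutting follow-up at 30 months in the simulation gives slightly stronger OS bias: 0.77 to 0.83 with all removed and 0.89 to 0.92 with half.

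With equal removal in both groups the simulated hazard ratios stay at about 1.00. The assumed 5.0-month PFS median rises to 6.9 months at an OS median of 8, and to 6.3 at 12.

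**4. Context.** If every patient had an event, 160 to 200 events would detect a hazard ratio of about 0.64 to 0.67 between regimens with 80% power at two-sided 0.05. The bias alone would therefore seldom reach significance, but it would shift the estimate.

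**The case against.** A reader might infer that whoever screens patients can already see survival. The documents do not say so. No section names the screener or the timing, and the prospective wording describes entry before outcomes exist. On that reading Inclusion 5 is an ordinary criterion. This stands, and it makes the point conditional. It does not remove the point, because the retrospective label and Inclusion 7 allow the other reading and nothing guards against it.

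Consent narrows the route further. If it is sought after treatment, early deaths are already out. If it is taken at baseline, eligibility would normally be judged then. Hindsight exclusion therefore needs consent before death and eligibility completed afterwards. Inclusion 7 permits that sequence, but the plan does not describe it.

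A reader might also infer that exclusions could be steered by molecular subtype. Section 1.1 puts classification after enrolment and sampling, so deliberate steering by subtype is not supported.

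Finally, the larger hazard-ratio figures need every early death to be removed from one regimen and none from the other. Nothing in the plan suggests that. The constant hazard may also overstate early deaths among patients already limited to ECOG 0–2 and able to tolerate chemotherapy.

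**Conclusion.** The concern holds conditionally. Three subjective, undated criteria sit in a study that calls itself retrospective, with no log and no check on eligibility. If they are applied after the outcome is known, early deaths can be excluded in hindsight.

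Equal exclusion inflates absolute PFS and OS (median OS by up to 3 months under the exponential assumption) and leaves the hazard ratio near 1.00. Unequal exclusion by regimen biases the comparison. The worst-case OS hazard ratio is about 0.78 to 0.87 with no true effect, and about 0.90 to 0.93 if half are removed. PFS gives about 0.80 to 0.88 and 0.90 to 0.94. All of these rest on assumed medians and constant hazards; they bound the problem and do not predict it.

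The documents do not show that any patient has been or will be excluded this way. The plan should be changed, but the point does not invalidate the study.

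**What to change.** 1. For any patient whose first-line treatment began before enrolment, drop Inclusion 5, Exclusion 4 and the compliance clause of Inclusion 8, or apply them only where the judgement was documented in the chart before cycle 1.
2. Determine eligibility from dated pre-treatment records, before subtype results are linked.
3. Report every exclusion, with its reason, by regimen.
4. State whether entry is retrospective, prospective or mixed, and reconcile Inclusion 7 and the consent requirement with that statement. Both can remove early deaths by themselves, so changing the three judgement items alone would restore only some of them.

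The cost is the wording of three criteria, a short statement on timing and an exclusion table. A separate outcome-blind assessor would add protection but may need extra staff, and the steps above do not depend on one. The downside is that some patients with poor prognosis stay in, so PFS and OS may look slightly less favourable.
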